3.5 Pharmacokinetic Assessment

3.5.1 Sample Collections for Pharmacokinetic Analysis

PK analysis of serum iron, baseline corrected serum iron, TSAT, transferrin, TIBC, UIBC, maltol and maltol glucuronide in children and adolescents aged 1 month to 17 years in the ferric maltol group.

PK blood sampling in the 2 - 17 yrs age groups:

On PK study Day 1 (Visit 2) and PK study Day 2 (Visit 3) for the first 12 subjects in each age group (2 yrs – 9 yrs, 10 yrs-17 yrs, respectively) who have been randomised to ferric maltol groups have baseline PK blood samples collected immediately prior to ferric maltol dosing (0 hr). Subjects will then have further PK blood samples collected at two (2) additional times between 0.5 hr and 6 hrs after dosing on Visit 2 and 3; the post-dose PK sample time collection windows will be 0.5-1h, 1.0-2.0 hrs, 2.0-3.0 hrs, 3.0-4.0 hrs and 4.0-6.0 hrs. For each individual subject, the post-dose PK blood sampling schedule will be the same on PK Day 1 and PK Day 2. Post-dose blood samples should be collected within the time windows allocated only.

N.B: samples should be taken at least 1.0 hr apart. For each individual subject, the post-dose PK blood sampling schedule will be the same on PK Day 1 and PK Day 2.

PK Sample Schedule	PK Sample Schedule	PK Sample Schedule	PK Sample Schedule	PK Sample Schedule
Scriedule	Group 1	Group 2	Group 3	Group 4
PK Day 1 and PK Day 2	(N=3)	(N=3)	(N=3)	(N=3)
Pre-dose (0h)	X	X	X	X
0.5 – 1 hour	X	X	7	
1 – 2 hours	x		х	
2 – 3 hours		X		X
3 – 4 hours		64	X	
4 – 6 hours				X

Post-dose blood samples should be collected within the time windows allocated only. Samples should be taken at least 1.0 hr apart.

PK blood sampling in the 1 m - < 2 yrs age groups:

Pre-assignment phase: All subjects in 1 m-< 2 yrs age group will enter a 1-day PK assessment day prior to entering the treatment phase. Pre-assignment PK Day, each subject has baseline PK urine samples collected immediately prior to ferric maltol dosing (0 h). Following this, subjects will take a single dose of 0.1 ml/kg ferric maltol under supervision. Three (3) PK urine samples will be taken between 0.5 hr -3 hrs, 3 hrs -6 hrs, and 7 hrs -12 hrs post dose. N.B: samples should be taken at least 1.0 h apart.

PK Day 2 (Visit 3), each subject has baseline PK blood and urine samples collected immediately prior to ferric maltol dosing (0 h). Following this, subjects will take a single dose of

0.1 ml/kg ferric maltol under supervision. Three PK Post-dose blood samples will be collected at the following windows 1.0-2.0 hrs, 3.0-4.0 hrs and 10.0-12.0 hrs; postdose urine samples will be taken between 0.5 hr -3 hrs, 3 hrs -6 hrs and 7 hrs -12hrs post dose.

In the event of an administered dose not being consumed or partially consumed by the patient this will be noted as a missed dose and will not be repeated.

3.5.2 Handling Missing or Below the Lower Limit of Quantification Data

In the event of an administered dose not being consumed or partially consumed by the patient this will be flagged.

If the actual sampling time is missing, but a valid concentration value has been measured, the concentration value will be flagged, and the scheduled time point may be used for the calculation of PK parameters. If the nominal timepoint is a range (e.g., 4-6 hours), the midpoint will be used for the missing timepoint.

If the dosing history information for a subject is missing, the sampling for that subject relative to the missing dosing period will be flagged and not be included in summary statistics. For other cases (i.e., missing pre-dose beyond the first dose of the treatment group), missing data will not be imputed.

In individual concentration and PK parameter calculations employing the naive-pooled approach, BLQ values are treated as follows:

- If BLQ values occur at pre-dose will be assigned as zero
- All other instances of BLQ values, beyond the first predose, will be set as missing.

The following general rules will be applied for the concentration summary for each period:

 In cases where a mean value is not calculated, due to more than half (>50%) of the values at schedule time point are BLQ or missing, the mean value will be set to BLQ for the summary table.

3.5.3 Pharmacokinetic Concentration

The following PK concentrations for the two age groups, 2-17 yrs and 1 m - < 2 yrs, will be determined and the observed values will be summarised by age group, formulation / condition, and by visit/timepoint for PK Population using the following statistics: n (the number of subjects), geometric mean, geometric standard deviation (SD), coefficient of variation (CV), median, minimum and maximum. The observed data will also be listed by age group, formulation / condition group for each individual subject for PK Population.

If the PK data for any age group is too limited and does not support summary statistics, only listings will be provided.

For age group 2-17 yrs, the mean observed plasma concentrations will be plotted on a linear and semi-logarithmic scale against nominal time range, formulation / condition. Geometric mean observed plasma concentrations will also be plotted on a linear scale against nominal time range by formulation/condition.

If the PK data for any age group is too limited and does not support summary statistics (i.e., mean and geomean), only individual concentrations will be plotted.

Individual observed concentrations will be plotted on a linear and semi-logarithmic scale against actual timepoint for each formulation/condition. Due to the sparse collection of data, all individuals within an age group will be plotted on the same plot.

2 - 17 yrs age groups:

 Plasma maltol and maltol glucuronide, serum iron, baseline corrected serum iron, transferrin, transferrin saturation (TSAT), total and unsaturated iron binding capacity (TIBC, UIBC).

1 m - < 2 yrs age groups:

 Serum iron, baseline corrected serum iron, total and unsaturated iron binding capacity (TIBC,UIBC), transferrin, transferrin saturation (TSAT), plasma maltol and maltol glucuronide, urine concentration of maltol and maltol glucuronide.

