12.2.2 Secondary Endpoint Analyses

The following endpoints will be reported for each treatment group using descriptive statistics summarised by mean, median, and range, and 95% CIs where applicable, split by age group:

- PK analysis of serum iron, TSAT, transferrin, TIBC, UIBC, maltol and maltol glucuronide in children and adolescents aged 1 month to 17 years in the ferric maltol group
- Changes in iron markers from baseline to Week 12
- Achieving Hb concentration within normal range at Week 12
- Qualitative assessments from subject questionnaires that allow evaluation of the acceptability, palatability and ease of use
- For subjects aged 1 month to < 2 years; Maltol and maltol glucuronide in urine: Aeo-6h, Aeo-3h, Ae3-6h, DurineO-6h, DurineO-3h, DurineO-6h, CLR; Pre-assignment and PK Day 2

Categorical variables will be summarised for each treatment group via number and percentage in each category, split by age group:

- Achieving Hb concentration within normal range at Week 12

Qualitative assessments from subject questionnaires that allow evaluation of the acceptability, palatability and ease of use will be summarised appropriately.

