3.3.4 Demographic and Baseline Characteristics

The following demographic and baseline characteristics will be summarised:

- Age (years) and age categories (1 month to <2 years, 2 years to 9 years, 10 years to 17 years),
- Sex,
- Childbearing potential, if Female or Undifferentiated,
- Race.
- Ethnicity,
- Height/Length (cm),
- Weight

Body mass index (BMI) (kg/m²).

Demographic and baseline characteristics will be summarised with descriptive statistics or counts and percentages of subjects as appropriate by treatment and in total for all randomised/assigned subjects split by age categories of 1 month to 2 years and 2 years to 17 years.

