3.4.2 Secondary Endpoints Analysis

The secondary endpoints will be reported for each treatment group using descriptive statistics summarised by mean, median, and range (minimum and maximum), and 95% confidence interval for the mean where applicable, split by age group.

Any measurement obtained after a patient received a blood transfusion, or received an intravenous iron or erythropoiesis stimulating agent (ESA) will be excluded from the analysis.

The secondary endpoints are as follows: PK analysis of Serum Iron, Corrected serum iron, TSAT, Transferrin, TIBC, UIBC, Maltol and Maltol Glucuronide.

Descriptive summary statistics will be summarised for children and adolescents aged 1 month to 17 years in the ferric maltol group for the PK analysis of Serum Iron, Corrected serum iron, TSAT, Transferrin, TIBC, UIBC, Maltol and Maltol Glucuronide.

Changes in iron markers from baseline to Weeks 4 and 12

The secondary analysis of the change from baseline to Weeks 4 and 12 in iron markers (serum iron, serum corrected iron, transferrin, TSAT, TIBC, UIBC and ferritin) will be summarised using descriptive summary statistics. In this analysis, missing Week 12 and Week 4 values will be imputed using a LOCF (last observation carried forward) approach in which the last available post-baseline measurement will be used in the analysis.

Achieving Hb concentration within normal range at Week 12

The number and percentage of subjects achieving normal range, based on the central laboratory's normal reference range, at Week 12 will be summarised by treatment group.

Qualitative assessments from subject questionnaires that allow evaluation of the acceptability, palatability and ease of use

Qualitative assessments from subject questionnaires that evaluate acceptability, palatability and ease of use will be summarised separately for children aged 5 and under and those aged 6 and over.

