3.5.4 Pharmacokinetic Parameters

The following PK parameters will be determined for the 2 – 17 yrs age groups using a naïve pooled approach on PK Day 1 and Day 2:

 PK analysis of serum iron, corrected serum iron, maltol and maltol glucuronide in the ferric maltol group.

Parameters	Description	Precision
Cmax	Maximum plasma concentration; determined directly from the concentration time profile; if the maximum plasma concentration occurs at more than one time point, C _{max} is defined as the first maximum value	sig/3
T _{max}	Time to C_{max} ; If the maximum value occurs at more than one time point, T_{max} is defined as the first time point with this value.	dec/2
AUClast	Area under the plasma concentration vs time curve (AUC) from predose (time 0) to the last quantifiable plasma concentration (C _{last})	sig/3
AUCinf	AUC from time 0 to infinity; calculated as (AUC _{last} + C _{last} /λz)	sig/3
t _{1/2}	Apparent first-order terminal elimination half-life; calculated as ln(2)/λz	dec/2

Note: "Precision" is defined as the default type (significant figures "sig" or decimal places "dec") and value that will be displayed in outputs unless specifically defined elsewhere.

The Linear-Log Trapezoidal method (equivalent to the Linear Up/Log Down option in WinNonlin) will be used in the computation of all AUC values.

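### PK output for ages 2-17 has no classification by dose, although the dose per administration doubles at age 12, and the age grouping meant for PK is unclear

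*SAP*

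**What the plan says.** **Grouping for PK.** SAP 3.5.3 counts two groups: "PK concentrations for the two age groups, 2-17 yrs and 1 m - < 2 yrs, will be determined". Summaries are by age group, a formulation / condition label, and visit or timepoint. Means are plotted for the older group as a whole: "For age group 2-17 yrs, the mean observed plasma concentrations will be plotted on a linear and semi-logarithmic scale". In the individual plots, "all individuals within an age group will be plotted on the same plot". For sparse data: "If the PK data for any age group is too limited and does not support summary statistics, only listings will be provided". SAP 3.5.4 derives Cmax, Tmax, AUClast, AUCinf and half-life for the 2-17 years "age groups using a naïve pooled approach on PK Day 1 and Day 2".

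**General rule for secondary endpoints, which include PK.** SAP 3.4.2 asks for descriptive statistics and a "95% confidence interval for the mean where applicable, split by age group". Protocol 12.2.2 asks for "mean, median, and range, and 95% CIs where applicable, split by age group". Neither says which age groups are meant.

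**Age groups elsewhere.** SAP 3.5.1 samples the first 12 ferric maltol subjects in each of ages 2-9 and 10-17. SAP 3.3.4 lists "age categories (1 month to <2 years, 2 years to 9 years, 10 years to 17 years" as categories, but splits the demographic tables at 2 years only.

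**Dose.** SAP 2.2.3 and Protocol 5.5.2 give 15 mg per dose at ages 2-11 and 30 mg at ages 12-17. Protocol 7.1 applies the same step on the PK days.

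**The concern.** PK in ages 2-17 is a secondary objective, and these tables would be read as exposure at the studied doses. The older PK group contains two doses that differ by a factor of two, and no planned summary, plot or parameter separates them.

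The formulation / condition label does not do so. The SAP does not define it. In Protocol 5.5 it belongs to the adult study of capsule against suspension, fed and fasted. This trial has one ferric maltol formulation.

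Reading the rule as ages 2-9 and 10-17 helps only in part. Ages 2-9 are all on 15 mg, but 10-17 mixes doses if its PK children include both some aged 10-11 and some aged 12 or older. Randomisation is stratified at 9/10 years (Protocol 7.1), so nothing fixes that mix.

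If exposure differs by dose, a pooled value falls between the two dose levels, at a point set by how many PK children happen to be 12 or older.

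**Working it through.** **1. The plan's own counts reproduce.** 12 × 2 = 24 PK children (SAP 2.2.4). In the sampling table each age group gives 6 + 6 + 6 + 3 + 3 = 24 post-dose samples per PK day, which equals 12 children × 2. At 30 mg per 5 ml, or 6 mg/ml, 2.5 ml is 15 mg and 5 ml is 30 mg.

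**2. How many are on 30 mg.** The documents allow 0 to 12 of the 24. If ages 10-17 were evenly spread (assumption), six of eight years of age are on 30 mg, so the count is Binomial(12, 0.75). Its mean is 9, P(6 to 12) = 0.986 and P(12) = 0.032. The illustration therefore uses 6 to 12.

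**3. Which analytes.** Protocol 5.4.3 (ages 10-17; 7.8, 16.6 and 30 mg) reports that maltol glucuronide was dose-proportional, with Day 10 Cmax deviating slightly, and that no tested covariate affected its CL/F. Iron was not dose-proportional. It probably plateaued between 16.6 and 30 mg on Day 1 and was comparable across doses on Day 10.

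**4. Effect on a pooled geometric mean.** Let R be the assumed 30:15 mg exposure ratio and f the share of children on 30 mg, with the same dose mix in every sampling window. Pooled mean relative to 15 mg = R^f; relative to 30 mg = R^(f-1). The three values in each cell are for f = 6/24, 9/24 and 12/24.

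| R | relative to 15 mg | relative to 30 mg |
|---|---|---|
| 2 | 1.189, 1.297, 1.414 | 0.595, 0.648, 0.707 |
| 1.41 | 1.091, 1.139, 1.189 | 0.771, 0.805, 0.841 |
| 1.25 | 1.057, 1.087, 1.118 | 0.846, 0.870, 0.894 |
| 1 | 1, 1, 1 | 1, 1, 1 |
| 0.8 | 0.946, 0.920, 0.894 | 1.182, 1.150, 1.118 |

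**5. Ages 10-17 alone.** At R = 2 with f = 6/12, 9/12 and 11/12, the values are 1.414, 1.682 and 1.888 relative to 15 mg, and 0.707, 0.841 and 0.944 relative to 30 mg. With 0 or 12 of 12 on 30 mg there is no mixing in this group.

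**6. The mix can vary by window.** Pooled over 2-17, six children supply each of the 3-4 h and 4-6 h windows: three aged 2-9, all on 15 mg, and three aged 10-17. With 0 to 3 of the latter on 30 mg, the window mean at R = 2 runs from 1.00 to 1.41 times the 15 mg value. Step 4 therefore illustrates the effect; it does not predict a naive-pooled Cmax or AUC. SAP 3.5.4 also does not say which mean is pooled.

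**7. Half-life.** Log-linear fits at 2.5, 3.5 and 5 h were run over all allocations, with an assumed true value of 1.1 h. The median stays at 1.10 h for R = 2, 1.41 and 1.25. At R = 2 with 9 children on 30 mg, pooled over 2-17, the 5th to 95th percentiles are 1.02 to 1.18 h. Dose mixing adds scatter but no systematic shift.

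**The case against.** A reader might infer that SAP 3.5.3 contradicts SAP 3.4.2. The documents do not support that. Neither SAP 3.4.2 nor Protocol 12.2.2 names its groups, and infants against ages 2-17 is an age split, essentially the one SAP 3.3.4 uses for demographics. Palatability uses yet another cut (5 and under, 6 and over). The headings in 3.5.3 and 3.5.4 also speak of 2-17 years age groups in the plural. What stands is that the PK grouping is ambiguous.

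A reader might also infer that pooled exposures will be wrong by up to 41%. That rests on R = 2, which has support within ages 10-17 for maltol glucuronide but little across 2-17. Doses are fixed rather than per kg, and no PK data below age 10 are reported. With assumed weights of 12 kg at age 2 and 36 kg at age 11, 15 mg is 1.25 to 0.42 mg/kg. At an assumed 40 to 60 kg, 30 mg is 0.75 to 0.50 mg/kg, inside that range. R could be near or below 1, and much of the heterogeneity could lie within the 15 mg group. This stands.

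Three further points carry weight. Six of the eight PK analytes are iron measures. The PK analysis is descriptive, with no test or decision attached. Individual data are listed and dose follows from age, so a split could be made later. Pooling is also a reasonable response to sparse sampling. These points limit the importance of the gap but do not close it: no planned output shows exposure at either dose, and showing both views avoids having to choose between pooling and splitting.

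**Conclusion.** The concern holds in a limited form. It is certain that the PK sections of the SAP have no dose class, that the formulation / condition label does not supply one, and that the age grouping for PK is not clearly stated.

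The consequence is conditional. It concerns Cmax, AUC and mean concentrations of maltol glucuronide, and possibly maltol. Serum iron is much less affected, and half-life is not systematically shifted. For a geometric mean with a constant dose mix and 6 to 12 of 24 children on 30 mg:

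- R = 2: +19% to +41% against the 15 mg value, and -41% to -29% against the 30 mg value.
- R = 1.25: +6% to +12%, and -15% to -11%.
- R = 1: no change.
- R below 1: the sign reverses.

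The documents cannot fix R across ages 2-17. This is a worthwhile, inexpensive improvement to a descriptive secondary analysis. It does not affect the primary endpoints.

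**What to change.** In SAP 3.5.3 and 3.5.4:

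- Add dose received (15 mg / 30 mg) as a class for summaries, plots, listings and naive-pooled parameters of maltol and maltol glucuronide, next to the pooled 2-17 output.
- Extend the existing fallback to listings and individual plots, now worded per age group, to any dose group that is too sparse.
- State which age groups the split in SAP 3.4.2 means for PK.
- Define or delete the formulation / condition label.

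Dose-normalising across 2-17 is not a substitute, because proportionality over that age range has not been shown. No change of dose is implied.

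**Cost.** SAP wording and some reprogramming; no new samples. The 30 mg group may be small. With 6 to 12 children it averages 6 × 3/12 = 1.5 to 12 × 3/12 = 3 samples in each of the two late windows. With n children on 30 mg, and the four schedule groups of three applied within each age group (assumption), the share of allocations leaving at least one late window empty is [2·C(9,n) - C(6,n)] / C(12,n). That is 48% for n = 4, 18% for 6, 4% for 8, 1% for 9 and 0% from 10. AUCinf and half-life at 30 mg may therefore be imprecise or not estimable. The 15 mg group would still span ages 2 to 11 at one fixed dose, so the split reduces heterogeneity without removing it.

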To assess the impact of a test meal on the PK of ferric maltol, an ANOVA model was performed on the In-transformed PK parameters (C_{max} , AUC_{last} , and AUC_{inf}) of the 2 formulations including terms for sequence (treatment sequence), treatment (formulation/condition), and period as fixed effects, and subjects nested within a sequence as a random effect.

For the capsule formulation, the ratios of C_{max} , AUC_{last} , and AUC_{inf} geometric LS means (90% CI) were 147.27% (130.01, 166.81), 134.25% (121.86, 147.91), and 137.53% (114.45, 165.26), respectively, comparing fasted versus fed conditions. These findings indicate that a food effect was observed for ferric maltol capsule with respect to C_{max} but a definitive food effect was not observed with respect to AUC_{last} and AUC_{inf} .

For the suspension formulation, the ratios of C_{max} , AUC_{last} , and AUC_{inf} geometric LS means (90% CI) were 103.93% (91.75, 117.72), 107.32% (97.41, 118.24), and 96.10% (76.45, 120.79), respectively, comparing fasted versus fed conditions. These findings indicate that the ferric maltol suspension had similar PK when administered in fasted or fed conditions with respect to C_{max} and AUC_{last} .

This Phase 3 open-label, comparative study is in the Paediatric Investigational Plan (PIP), designed to evaluate the safety, efficacy and tolerability of ferric maltol oral suspension compared to ferrous sulfate oral liquid over a 12 weeks treatment period in children and adolescents aged between 2 and 17 years. In order to comply with the iPSP agreed with FDA, children from 1 month to less than 2 years will be included in only the ferric maltol group. Due to the isoform of the glucuronidation enzyme, infants will initially receive only a single dose of ferric maltol. If the data from the single dose in this age group shows evidence of absorption of serum iron and elimination of maltol, subjects will enter a Treatment phase and be assigned to the ferric maltol arm. Subjects will be eligible to enter the treatment phase if the maltol level returns to baseline, or to a low level, confirming there is no accumulation of maltol or maltol glucuronide and there is evidence of iron absorption.

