7 INVESTIGATIONAL PLAN

7.1 STUDY OVERVIEW

This is a Phase 3, randomised, open-label, active controlled, multicentre, comparative study between ferric maltol oral suspension and ferrous sulfate oral liquid. 98 eligible subjects aged 2 to 17 years will be randomised at a ratio of 1:1 to ferric maltol or ferrous sulfate for a 12 weeks treatment period and a maximum of 12 subjects aged 1 month to < 2 years will be assigned to the ferric maltol group.

The study will comprise of the following stages:

- Screening: To determine subject eligibility for the study (within 21 days prior to the randomisation for each subject)
- Pre-assignment PK phase: only applicable for subjects aged 1 month to less than 2 years. Up to 28 days from Screening visit.

All eligible subjects aged 1 month to less than 2 years will enter a Pre-assignment phase, 1-day Pharmacokinetic assessment day following a single dose of ferric maltol oral suspension. After a baseline pre-dose urine sample, subjects will take a single dose of 0.1 ml/kg ferric maltol suspension under supervision and then further urine samples from three timepoints up to 12 hours.

The PK samples will be analysed and if evidence of metabolism and elimination of maltol is shown, these subjects will enter the treatment phase and be assigned to the ferric maltol arm. Subjects will be eligible to enter the treatment phase if the maltol level returns to baseline, or to a level confirming there is no accumulation of maltol or maltol glucuronide.

• Randomised treatment: 12 weeks open label treatment

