12.2 STATISTICAL METHODS

Full details of the statistical analysis, including the analysis of PK endpoints, will be specified in the statistical analysis plan.

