2.3.2 Secondary Endpoints

- PK analysis of serum iron, corrected serum iron, TSAT, TIBC, transferrin UIBC, maltol and maltol glucuronide in children and adolescents aged 1 month to 17 years in the ferric maltol group.
- Changes in iron markers from baseline to Week 4.
- Changes in iron markers from baseline to Week 12.
- Achieving Hb concentration within normal range at Week 12.
- Qualitative assessments from subject questionnaires that allow evaluation of the acceptability, palatability and ease of use.
- For subjects aged 1 month to < 2 years; maltol and maltol glucuronide in urine from both PK days in children aged 1 month to less than 2 years.

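### The SAP leaves out the protocol's infant urine parameters (Ae, Durine, CLR) without declaring it, and urine concentration alone cannot quantify how much maltol is excreted

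*SAP*

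**What the plan says.** **Protocol.** Section 12.2 leaves the PK detail to the SAP: "Full details of the statistical analysis, including the analysis of PK endpoints, will be specified in the statistical analysis plan". Section 12.2.2 then lists the infant urine quantities: "Maltol and maltol glucuronide in urine: Aeo-6h, Aeo-3h, Ae3-6h, DurineO-6h, DurineO-3h, DurineO-6h, CLR; Pre-assignment and PK Day 2". The text as read is partly garbled, and one Durine interval appears twice, which may be a PDF-reading artefact. The protocol's abbreviation index does not define these symbols. I read Ae as amount excreted, CLR as renal clearance, and Durine as a measure of dose recovered in urine.

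Section 5.5 explains why this age group is handled separately: "Due to the isoform of the glucuronidation enzyme, infants will initially receive only a single dose of ferric maltol". Section 10.4 schedules a pre-dose urine sample and three post-dose samples (0.5-3 h, 3-6 h, 7-12 h) on both infant PK days. PK blood is scheduled on PK Day 2 only.

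**SAP.** Section 2.3.2 keeps the endpoint ("maltol and maltol glucuronide in urine from both PK days in children aged 1 month to less than 2 years") but names no parameter. Section 3.4.2 has no entry for infant urine. Section 3.5.3 lists the infant analytes and ends with "plasma maltol and maltol glucuronide, urine concentration of maltol and maltol glucuronide". Section 3.5.4 covers "PK analysis of serum iron, corrected serum iron, maltol and maltol glucuronide in the ferric maltol group" for ages 2 to 17 only, with Cmax, Tmax, AUClast, AUCinf and half-life. Section 5 declares two changes: the mITT population for the haemoglobin analysis and the Week 4 iron markers.

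**The concern.** The protocol names quantities and sends their specification to the SAP. The SAP does not mention them and does not say that they were dropped. Under SAP 3.5.4 infants receive no derived PK parameter of any kind, in plasma or urine. This is the cohort in which the handling of maltol is the open question, and on the Pre-assignment day urine is the only source of maltol data.

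What remains, raw concentration, depends on how much urine was produced as well as on how much maltol was excreted. Two infants who excrete the same amount can differ in concentration because of hydration or feeding. So can one infant on the two PK days. At stake is whether the reported secondary endpoint can say anything quantitative about infant excretion, and whether a reader of the study report can see that protocol-named parameters were not produced.

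**Working it through.** **1. Side by side.**

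| Infant urine item | Protocol 12.2.2 | SAP |
|---|---|---|
| Ae by interval within 0-6 h | named, both PK days | absent |
| Durine by interval within 0-6 h | named, both PK days | absent |
| CLR | named, both PK days | absent |
| Concentration | not named there (objective 3 in section 6.2 uses the word) | summarised and listed (3.5.3) |
| Declared as a change | not applicable | no (section 5) |

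The plan gives no sample-size, power or alpha figure on this point, so there is none to reproduce.

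**2. Effect of dilution (illustration; amounts and volumes are assumed).** Concentration = amount / volume. Take 1000 units excreted, 98% as glucuronide: 980 units glucuronide and 20 units maltol.

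| Urine volume | Glucuronide conc. | Maltol conc. | Ratio | Amount excreted |
|---|---|---|---|---|
| 20 mL | 980/20 = 49.0 | 20/20 = 1.00 | 49 | 1000 |
| 40 mL | 980/40 = 24.5 | 20/40 = 0.50 | 49 | 1000 |
| 60 mL | 980/60 = 16.3 | 20/60 = 0.33 | 49 | 1000 |

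Concentration moves 3-fold with the amount fixed. The within-sample ratio does not move, because volume cancels.

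**3. What the collection windows cover.** They span 2.5 + 3 = 5.5 of the first 6 h, and 2.5 + 3 + 5 = 10.5 of 12 h. The periods 0-0.5 h and 6-7 h fall outside. To size this, assume first-order excretion from the time of dosing with no absorption delay: share between times a and b = exp(-ka) - exp(-kb), with k = ln 2 / half-life. The 1.1 h half-life is the adult glucuronide figure in Protocol 5.4.2 (ST10-01-102). The 2 h and 4 h values are assumptions.

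| Half-life | 0-0.5 h | 0-6 h | 7-12 h |
|---|---|---|---|
| 1.1 h | 27.0% | 97.7% | 1.2% |
| 2 h | 15.9% | 87.5% | 7.3% |
| 4 h | 8.3% | 64.6% | 17.2% |

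Ignoring absorption overstates the 0-0.5 h share. The 7-12 h sample matters little at the adult half-life and more if elimination is slower, yet the protocol's list, as read, stops at 6 h.

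**4. Could dilution hide slow elimination?** Between the window mid-points, 1.75 h and 9.5 h, the excretion rate falls by 2^(7.75 / half-life). Allow an assumed 3-fold difference in dilution in either direction:

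- 1.1 h: 132-fold, range 132/3 = 44 to 132 x 3 = 396
- 2 h: 14.7-fold, range 4.9 to 44
- 3 h: 6.0-fold, range 2 to 18
- 4 h: 3.8-fold, range 1.3 to 11.5

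The 3 h and 4 h ranges do not reach the adult range, and the 2 h range only touches it.

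**5. Which parameters can be derived?** Ae and Durine need a urine volume for each collection. Whether volume is recorded would be in the Laboratory Manual, which is not among the documents. CLR also needs plasma exposure. The Pre-assignment day has no PK blood sample, so CLR cannot be obtained for that day. On PK Day 2 it would need an infant plasma AUC, which the SAP does not plan.

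**The case against.** The strongest defence is that the SAP matches the stated objective. Objective 3 speaks of urine concentration in both documents, the endpoint says only that the two analytes are measured in urine, and the synopsis promises a summary per PK day. The gap is confined to one parameter list, for a descriptive endpoint in at most 12 infants, and the protocol allows the study to finish without that cohort. If the samples are spot urines, Ae cannot be computed at all. All of this limits the stakes. It does not remove the mismatch with Protocol 12.2.2 or explain why section 5 is silent.

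A reader might infer three stronger things that the documents do not support.

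- *That concentrations cannot show metabolism or elimination at all.* They can, qualitatively. Glucuronide in post-dose urine, set against the pre-dose sample, is evidence of both, and SAP 3.5.3 lists observed values for each infant.
- *That the omission drives entry to the treatment phase.* Protocol 7.1 makes entry depend on the samples ("The PK samples will be analysed and if evidence of metabolism and elimination of maltol is shown"). Protocol 9.2 has the results assessed infant by infant, with a Medical Monitor recommendation and the investigator's decision. SAP summaries do not set that step.
- *That a slow eliminator could pass for normal.* Step 4 of the working largely rules this out at 3-fold dilution. It also uses the glucuronide half-life. Maltol's own adult half-life of 0.8 h gives a fall of about 825-fold over the same interval.

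**Conclusion.** The point holds as an undeclared omission with a limited analytical cost. Three protocol-named quantities (Ae, Durine, CLR) are missing from the SAP for both infant PK days, and no derived infant PK parameter replaces them. Concentrations give qualitative evidence of metabolism and elimination. They do not measure the amount excreted, and they confound comparisons between infants and between days with dilution. The 3-fold figure rests on assumed volumes of 20 to 60 mL. The direction follows from the definition of concentration and needs no assumption.

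The harm is to the reported secondary endpoint and to traceability between protocol and SAP. It does not extend to the treatment-entry decision. The change should be made, but the primary analyses are not affected.

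**What to change.** **SAP 3.5.4, for both infant PK days:**

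1. Report the maltol glucuronide-to-maltol ratio in each urine sample, stating whether it is by mass or molar. When maltol is below quantification, report the ratio as a lower bound, using the quantification limit as the denominator. This needs its own rule, because SAP 3.5.2 sets post-dose values below quantification to missing in its calculations. Do not compute a ratio when both analytes are below quantification.
2. Where collection volume was recorded, report Ae for each interval as concentration times volume, including 7-12 h. State that 0-0.5 h and 6-7 h fall outside the windows, how incomplete collections are flagged, and that they make Ae approximate. Where no volume exists, report the ratio only.

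**SAP section 5:** declare each protocol parameter that cannot be derived, with the reason. CLR on the Pre-assignment day has no plasma sample. CLR on PK Day 2 has no planned infant plasma AUC (add one, or declare the omission). Ae and Durine cannot be derived where volumes are missing. Clear up the repeated Durine interval at the same time.

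**Cost:** a few SAP lines and a few derived variables. The ratio needs no new sample or assay. Ae depends on volumes that may or may not exist. If the database is already locked, SAP section 1 directs that deviations be documented in the study report, and the same text can go there.
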